## 8. ETHICAL AND REGULATORY REQUIREMENTS

### 8.1 Ethical conduct of the study

The study will be performed in accordance with ethical principles that have their origin in the Declaration of Helsinki and are consistent with ICH/Good Clinical Practice, applicable regulatory requirements and the AstraZeneca policy on Bioethics and Human Biological Samples.

### 8.2 Patient data protection

The Informed Consent Form will incorporate (or, in some cases, be accompanied by a separate document incorporating) wording that complies with relevant data protection and privacy legislation.

### 8.3 Ethics and regulatory review

An Ethics Committee should approve the final study protocol, including the final version of the Informed Consent Form and any other written information and/or materials to be provided

to the patients. The investigator will ensure the distribution of these documents to the applicable Ethics Committee, and to the study site staff.

The opinion of the Ethics Committee should be given in writing. The investigator should submit the written approval to AstraZeneca before enrolment of any patient into the study.

The Ethics Committee should approve all advertising used to recruit patients for the study.

AstraZeneca should approve any modifications to the Informed Consent Form that are needed to meet local requirements.

If required by local regulations, the protocol should be re-approved by the Ethics Committee annually.

Before enrolment of any patient into the study, the final study protocol, including the final version of the Informed Consent Form, is approved by the national regulatory authority or a notification to the national regulatory authority is done, according to local regulations.

AstraZeneca will handle the distribution of any of these documents to the national regulatory authorities.

AstraZeneca will provide Regulatory Authorities, Ethics Committees and Principal Investigators with safety updates/reports according to local requirements, including SUSARs (Suspected Unexpected Serious Adverse Reactions), where relevant.

## **8.4 Informed consent**

The Principal Investigator(s) at each centre will:

- Ensure each patient is given full and adequate oral and written information about the nature, purpose, possible risk and benefit of the study
- Ensure each patient is notified that they are free to discontinue from the study at any time
- Ensure that each patient is given the opportunity to ask questions and allowed time to consider the information provided
- Ensure each patient provides signed and dated informed consent before conducting any procedure specifically for the study
- Ensure the original, signed Informed Consent Form(s) is/are stored in the ISF
- Ensure a copy of the signed Informed Consent Form is given to the patient

- Ensure that any incentives for patients who participate in the study as well as any provisions for patients harmed as a consequence of study participation are described in the informed consent form that is approved by an Ethics Committee.

## **8.5 Changes to the protocol and informed consent form**

Study procedures will not be changed without the mutual agreement of the co-ordinating investigator and AstraZeneca.

If there are any substantial changes to the study protocol, then these changes will be documented in a study protocol amendment and where required in a new version of the study protocol (Revised Clinical Study Protocol).

The amendment is to be approved by the relevant Ethics Committee and if applicable, also the national regulatory authority approval, before implementation. Local requirements are to be followed for revised protocols.

AstraZeneca will distribute any subsequent amendments and new versions of the protocol to each Principal Investigator(s). For distribution to Ethics Committee see Section 8.3.

If a protocol amendment requires a change to a centre's Informed Consent Form, AstraZeneca and the centre's Ethics Committee are to approve the revised Informed Consent Form before the revised form is used.

If local regulations require, any administrative change will be communicated to or approved by each Ethics Committee.

## **8.6 Audits and inspections**

Authorised representatives of AstraZeneca, a regulatory authority, or an Ethics Committee may perform audits or inspections at the centre, including source data verification. The purpose of an audit or inspection is to systematically and independently examine all study-related activities and documents, to determine whether these activities were conducted, and data were recorded, analysed, and accurately reported according to the protocol, Good Clinical Practice (GCP), guidelines of the International Conference on Harmonisation (ICH), and any applicable regulatory requirements. The investigator will contact AstraZeneca immediately if contacted by a regulatory agency about an inspection at the centre.

# **9. STUDY MANAGEMENT BY ASTRAZENECA**

## **9.1 Pre-study activities**

Before the first patient is entered into the study, it is necessary for a representative of AstraZeneca to visit the investigational study site to:

- Determine the adequacy of the facilities

- Determine availability of appropriate patients for the study
- Discuss with the investigator(s) (and other personnel involved with the study) their responsibilities with regard to protocol adherence, and the responsibilities of AstraZeneca or its representatives. This will be documented in a Clinical Study Agreement between AstraZeneca and the investigator.

## 9.2 Training of study site personnel

Before the first patient is entered into the study, an AstraZeneca representative will review and discuss the requirements of the Clinical Study Protocol and related documents with the investigational staff and also train them in any study-specific procedures and the WBDC system utilised.

The Principal Investigator will ensure that appropriate training relevant to the study is given to all of these staff, and that any new information relevant to the performance of this study is forwarded to the staff involved.

The Principal Investigator will maintain a record of all individuals involved in the study (medical, nursing and other staff).

## 9.3 Monitoring of the study

During the study, an AstraZeneca representative will have regular contacts with the study site, including visits to:

- Provide information and support to the investigator(s)
- Confirm that facilities remain acceptable
- Confirm that the investigational team is adhering to the protocol, that data are being accurately and timely recorded in the eCRFs, that biological samples are handled in accordance with the Laboratory Manual and that study drug accountability checks are being performed
- Perform source data verification (a comparison of the data in the eCRFs with the patient's medical records at the hospital or practice, and other records relevant to the study) including verification of informed consent of participating patients. This will require direct access to all original records for each patient (eg, clinic charts)
- Ensure withdrawal of informed consent to the use of the patient's biological samples is reported and biological samples are identified and disposed of/destroyed accordingly, and the action is documented, and reported to the patient.

The AstraZeneca representative will be available between visits if the investigator(s) or other staff at the centre needs information and advice about the study conduct.

### 9.3.1 Source data

Refer to the CSA for location of source data.

## 9.4 Study agreements

The Principal Investigator at each centre should comply with all the terms, conditions, and obligations of the Clinical Study Agreement, or equivalent, for this study. In the event of any inconsistency between this Clinical Study Protocol and the Clinical Study Agreement, the terms of the Clinical Study Protocol shall prevail with respect to the conduct of the study and the treatment of patients and in all other respects, not relating to study conduct or treatment of patients, the terms of the Clinical Study Agreement shall prevail.

Agreements between AstraZeneca and the Principal Investigator should be in place before any study-related procedures can take place, or patients are enrolled.

### 9.4.1 Archiving of study documents

The Investigator follows the principles outlined in the CSA.

## 9.5 Study timetable and end of study

The end of the study is defined as ‘the last visit of the last patient undergoing the study’.

The study is expected to start in \_\_\_\_\_ and to end by \_\_\_\_\_.

The study may be terminated at individual centres if the study procedures are not being performed according to GCP, or if recruitment is slow. AstraZeneca may also terminate the entire study prematurely if concerns for safety arise within this study or in any other study with AZD5069.

## 10. DATA MANAGEMENT BY ASTRAZENECA DATA MANAGEMENT CENTRE

Data management will be performed by AstraZeneca Data Management Centre (DMC) staff.

Data will be entered in the WBDC system at the study site. Trained study personnel will be responsible for entering data on the observations, tests and assessments specified in the protocol into the WBDC system and according to the eCRF Instructions. The eCRF Instructions will also guide the study site in performing data entry. Data queries will be raised for inconsistent, impossible or missing data. Data entered in the WBDC system will be immediately saved to a central database and changes tracked to provide an audit trail. The data will be validated as defined in the Data Management Plan. Quality control procedures will be applied to each stage of data handling to ensure that all data are reliable and have been processed correctly.

Site personnel will enter the data in the eCRFs. The data will then be Source Data Verified (SDV), reviewed/queried and updated as needed. The principal investigator will then sign the eCRF electronically. Clean file occurs when all data have been coded, validated, signed by the investigator, locked and declared clean. Any treatment revealing data may thereafter be frozen and then locked to prevent further editing. A copy of the eCRF will be archived at the study site when the study has been locked.

Medical coding is done using the most current version of Medical Dictionary for Regulatory Activities (MedDRA) and AstraZeneca Drug Dictionary. Adverse events and medical/surgical history will be classified according to the terminology of the latest version MedDRA. Medications will be classified according to the AstraZeneca Drug Dictionary. All coding will be performed by the Medical Coding Team at the AstraZeneca DMC.

The DMC will determine the format of third party data and coordinate the flow of data to an external environment or clinical database (if applicable). The DMC will ensure that the data collection tool (for eg, IVRS/IWRS) will be tested / validated as needed. The data collected through third party sources will be obtained and reconciled against study data.

SAE Reconciliation Reports are produced and reconciled with Patient Safety database and/or the Investigational Site.

Data associated with biological samples will be transferred to laboratories internal or external to AstraZeneca.

For details of genotype data handling refer to Appendix D.

## **11. EVALUATION AND CALCULATION OF VARIABLES BY ASTRAZENECA**

### **11.1 Calculation or derivation of safety variable(s)**

#### **11.1.1 Other significant adverse events (OAE)**

During the evaluation of the blinded AE data, an AstraZeneca medically qualified expert will review the list of AEs that were not reported as SAEs and DAEs. Based on the expert's judgement, significant adverse events of particular clinical importance may, after consultation with the Global Safety Physician, be considered OAEs and reported as such in the Clinical Study Report. A similar review of data from laboratory tests, vital signs, ECGs and other safety assessments will be performed for identification of OAEs.

Examples of these are marked haematological and other laboratory abnormalities, and certain events that lead to intervention (other than those already classified as serious) or significant additional treatment.

## 11.2 Calculation or derivation of patient reported outcome variables

No variables will be derived from the diary card data.

## 11.3 Calculation or derivation of pharmacokinetic variables

The PK analyses of the plasma concentration for AZD5069 will be performed at AstraZeneca R&D. The actual sampling times will be used in the PK calculations. Due to the sparse PK sampling employed for all but a sub-group of the patients, a population-PK approach will be used to derive the PK parameters, for which a full PK & PK/PD analysis plan will be written and finalised prior to database-lock. Briefly, the PK data from all patients using actual sample times will be used to build a population PK model and the individuals' PK parameters derived from a post-hoc estimation of the model to each individual's data. Where possible, the following PK parameters will be determined for AZD5069:

Maximum plasma concentration ( $C_{max}$ ), time to  $C_{max}$  ( $t_{max}$ ), terminal rate constant ( $\lambda_z$ ), terminal plasma half-life ( $t_{1/2}$ ), area under the plasma concentration-time curve from zero to the time of the last measurable concentration ( $AUC_{(0-t)}$ ) and from zero to infinity (AUC), plasma clearance (CL/F), volume of distribution during terminal phase ( $V_z/F$ ) and mean residence time (MRT).

For the calculation of PK parameters, plasma concentrations for AZD5069 prior to the first measurable concentration will be taken as zero. Plasma concentrations of AZD5069 below the limit of quantification (LOQ) that occur after the first measurable concentration will be excluded from the analysis. The resulting PK parameters will be estimated based on the whole profile.

## 11.4 Calculation or derivation of pharmacodynamic variable(s)

Circulating neutrophil counts will be assessed in blood samples.

### 11.4.1 Calculation or derivation of the relationship between pharmacokinetic and pharmacodynamic variables

The relationship between AZD5069 plasma concentration and the effect on circulating neutrophils in blood will be presented graphically. If appropriate, concentration-effect relationships will be explored using a population-PK/PD approach to link the population-PK model described in Section 11.3 to the neutrophil count data.

Additional analyses of potential relationships between AZD5069 dose, plasma concentration or exposure ( $C_{max}$ , AUC) and safety or clinical parameters may be performed if required.

## 11.5 Calculation or derivation of pharmacogenetic variables

See Appendix D for information on the pharmacogenetic research.

## **11.6 Calculation or derivation of health economic variables (Not applicable)**

Not applicable.

## **12. STATISTICAL METHODS AND SAMPLE SIZE**

### **12.1 Description of analysis sets**

#### **12.1.1 General principles**

The analysis of the data will be based on potentially different subsets according to the purpose of analysis, ie, for safety, PK and PD, respectively. The decision regarding validity of data for inclusion in each of the analysis sets will be based on blind review of the data.

The as-treated principle will be applied to all evaluations; ie, patients who received another treatment than the one assigned in the randomisation list will be analysed as belonging to the actual treatment group and not that assigned by randomisation.

#### **12.1.2 All subject analysis set**

This analysis set comprises all patients screened for the study and will be used for reporting of disposition and screening failures.

#### **12.1.3 Safety analysis set**

All patients who are randomised into the study and receive at least one dose of randomised investigational product, AZD5069 or placebo, and for whom any post-dose data are available will be included in the safety analysis set.

Throughout the safety analyses, erroneously treated patients (eg, those randomised to treatment A but actually given treatment B) will be accounted for in the actual treatment group.

#### **12.1.4 PK analysis set**

The PK analysis set will be based on the safety analysis set. The patients who are in the safety analysis set and provide evaluable PK data appropriate for the evaluation of interest (with no major protocol deviations or violations thought to significantly affect the pharmacokinetics of the drug) will be included in the PK analysis set. It may be that specific data points are not included in this analysis set due to deviations or violations at that specific time. Patients who receive placebo will not be part of the PK analysis set.

#### **12.1.5 PD analysis set**

The PD analysis set will be based on the safety analysis set. The patients who are in the safety analysis set and provide the evaluable PD data appropriate for the evaluation of interest (with no major protocol deviations or violations thought to significantly affect the PD assessment of the drug) will be included in the PD analysis set. It may be that specific data points are not

included in this analysis set due to deviations or violations at that specific time. Patients who receive placebo will be included in this analysis set.

## **12.2 Methods of statistical analyses**

### **12.2.1 General principles**

No formal statistical hypothesis testing will be performed.

Data will be presented by actual dose.

No action will be taken to handle missing data unless specified. The summaries of the data will show the number of data points and/or patients included. If a baseline value is missing, then the pre-treatment value taken closest to the scheduled baseline will be used.

A patient who withdraws prior to the last planned observation in a study period will be included in the analyses up to the time of discontinuation.

### **12.2.2 Patient characteristics**

Continuous variables will be summarised using descriptive statistics (eg, n, mean, standard deviation (SD), min, median, max) by treatment group. Categorical variables will be summarised in frequency tables (frequency and proportion) by treatment group.

Demographic data, medical and surgical histories, and physical examination data will be listed for all patients and summarised by treatment group using standard summary statistics.

Concomitant medications will be classified according to the AZ Drug Dictionary, the ATC system and the Committee for Medicinal Products for Human Use (CPMP) route of administration dictionary. All concomitant medications reported at entry and recorded during the study will be listed. Concomitant medications will be summarised by treatment group and ATC code using standard summary statistics, if there are sufficient data. This will be determined during the blind review of the data.

### **12.2.3 Safety and tolerability**

Safety data will be summarised based on the safety analysis set.

Continuous variables will be summarised using descriptive statistics (eg, n, mean, SD, min, median, max) by treatment group. Categorical variables will be summarised in frequency tables (frequency and proportion) by treatment group. Graphical presentations will be used as appropriate. Examples may include line graphs showing individual or mean development over time, shift plots showing baseline values on the horizontal axis and post-treatment values on the vertical axis.

Baseline will be the value measured and collected at Visit 2 prior to the first dose. If the measurement is missing, the latest pre-treatment measurement for each parameter will be

taken as baseline. For ECG parameters, vital signs and lung function tests, change from baseline at on- and post- treatment visits will be defined as: visit value-baseline value.

All adverse events will be collected for each patient from the time when informed consent is received until the follow-up visit (Visit 7). Adverse events will be considered as treatment emergent if they start or worsen on or after the first day of dosing, up to the post-study medical examination performed at Visit 7. AEs that occur before dosing will be reported separately. All AEs will be listed for each patient.

Adverse events will be summarised by PT (preferred term) and SOC (System organ class) using MedDRA vocabulary. Adverse events will also be summarised by causality and intensity, and causality and seriousness. Furthermore, listings of serious adverse events and adverse events that led to withdrawal will be made and the number of patients who had any adverse events, serious adverse events, adverse events that led to withdrawal, adverse events with severe intensity, other significant adverse events and deaths will be summarised.

ECG parameters will be summarised for the absolute values at each scheduled assessment, together with the corresponding changes from the baseline values. The QT correction factor will be based on the Fridericia's formula. Further categorical summaries of absolute QT and calculated QTcF values (>450 ms, >480 ms, >500 ms) and change from baseline values in QT and QTcF values (>30 ms, >60 ms) may also be produced.

All laboratory data will be listed. Deviations from extended and standard reference ranges quoted in project reporting ranges, will be explicitly noted on these listings where applicable. For parameters where there are no extended or standard reference ranges the reference range from the local laboratory will be used. Numerical laboratory data will be summarised using standard summary statistics for each treatment group at each visit. The change from baseline value will be similarly summarised. Discrete laboratory data will be summarised showing the number of patients at each level of measurement at each visit by treatment group. Summaries of the number of patients falling outside the reference ranges at each time point will also be provided by treatment group. Separate listings of only those values falling outside these reference ranges will also be produced.

Neutrophil counts will be summarised for the absolute value at each scheduled assessment together with the corresponding changes from the baseline value and the % changes from the baseline value. In addition, the maximum change and maximum % change from the baseline value will be summarised together with the assessment time the maximum changed occurred.

The following plots (please also refer to Section 12.2.6) will also be provided:

- Plots of mean value at each dose level of AZD5069 and placebo against time, symbols indicating dose level - medians will be used instead of means if the data is not normally distributed

- Plots of absolute values vs time (one plot per treatment group per data type showing separate lines for each patient, with a reference line added at the upper reference limit)
- Plots of change from baseline value vs time (one plot per treatment group per data type showing separate lines for each patient)
- Plots of % change from baseline value vs time (one plot per treatment group per data type showing separate lines for each patient).

Additional plots may produced if appropriate.

Pulse, systolic blood pressure, diastolic blood pressure and body temperature will be listed for each patient and summarised over time by treatment group using standard summary statistics. The change from baseline value will be similarly summarised. Summaries of the number of patients falling outside the reference ranges quoted on LDMS\_001\_0069526 “Standards for Collection and Evaluation of Laboratory and Vital Signs Safety Data in Clinical Studies”, at each time point will also be provided by treatment group.

Pre- and post- bronchodilator lung function tests will be listed for each patient and summarised over time by treatment group using standard summary statistics. The change from baseline will be similarly summarised.

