 Drug Substance AZD5069  
 Study Code D3550C00002  
 Edition Number 1  
 Date

analysis at twice daily time intervals eg, at 5.00 pm and 9.00 am until expiry at 72 hours post-sample collection. Exploratory leucocyte measurements taken at the central laboratory are for internal modelling use only and will not be reported in the CSR. Central laboratory leucocyte measurements will also only be available at the end of the study so as not to compromise the study blind.

The following will be assessed as part of the urinalysis dipstick: glucose, protein, blood. In addition, samples will be sent to the central laboratory for urine microscopy and quantitative measurements of total protein, albumin and creatinine if the local dipstick test for protein and/or blood is positive or if the urine sample appears abnormal on macroscopic examination, eg, if it is cloudy

Only for women under 50 years old, to confirm post-menopausal status

All women

Spirometry (lung function assessments) will be performed at the same time of day throughout the study  $\pm$ 2 hours relative to the time at baseline (Visit 2) pre- and 30 minutes post-bronchodilator

On PK days (Visits 2, 4, 5 and 6), blood samples for assessment of plasma PK and circulating leucocytes (including neutrophils) will be collected as far apart as possible (minimum of 90 minutes between samples) and patients should continue to take investigational product as per their normal schedule. Date and time of dose will be recorded in the electronic Case Report Form (eCRF) for Visit 2 and the first PK/leucocyte samples will be collected pre-dose. At Visit 3, 4, 5 and 6 the date and time of dosing on the clinic day and on the previous 2 days will be recorded in the eCRF.

Approximately 16 patients, at selected sites, will complete a PK sub-study. The patients will follow the same visit schedule as the main study but 3 of the clinic visits (Visits 2, 4 and 6) will be extended and the patient will remain at site for approximately 5 hours. Patients must not take investigational product (AZD5069 or placebo) at home on the morning of Visits 4 and 6. At these extended visits, 5 blood samples (pre-dose and then at approximately 1, 2, 3 and 5 hours post-dose) will be drawn for evaluation of plasma PK and blood samples (to match PK samples taken pre-dose [Visit 2 only], 1 and 3 hours post-dose) will be drawn for measurement of circulating leucocytes (including neutrophils). Further details can be found in Section 6.6

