AstraZeneca are proposing to discontinue patients from study medication if they have a high likelihood of having a sustained ANC below  $1 \times 10^9/L$ . AstraZeneca have defined “sustained” as a period greater than 24 hours but less than 48 hours. Patients who are found to have an ANC below  $1 \times 10^9/L$  or a leucocyte count below  $2 \times 10^9/L$  (according to local laboratory measurements) at any of their clinic visits will have a repeat blood sample taken in the afternoon of the following day (after 2:30 pm). The second test is in the afternoon because the circulating neutrophil numbers then are naturally higher than in the morning. Neutrophil numbers normally vary in a diurnal pattern, the numbers being lowest at around 8:00 am and highest around 8:00 pm. Diurnal fluctuations in the ANC/leucocyte count are still present in patients who have taken AZD5069.

If on repeat examination, the ANC/leucocyte count stopping criteria are still met, despite the second sample being taken when neutrophil levels are usually higher than in the morning, AZD5069 therapy will be discontinued. This is because AstraZeneca will assume that the ANC/leucocyte count is sustained even though the counts will not have been determined at the highest point of its daily cycle. Site staff should ensure that no patient takes more than 4 doses of study drug from the time of their initial abnormal blood test. Patients will be

informed by site staff (at enrolment and screening) that they should not take the morning dose of the study drug 2 days after the first abnormal blood test without first obtaining consent from the clinic (by telephone on the morning of the third day) that it is appropriate to do so.

Subjects who have missed and/or forgotten more than 3 consecutive doses should be referred to the AstraZeneca Study Physician for assessment as to whether the interruption in the Investigational Product constitutes discontinuation.

If a patient is withdrawn because of low neutrophil counts, the Investigator will monitor the blood count the following day and then at least every other day after that until the neutrophil numbers are within the local laboratory's reference range.

Specific reasons for discontinuing a patient from the genetic research are detailed in Appendix D.

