#### 6.4.5 Laboratory safety assessment

Blood and urine samples for determination of clinical chemistry, haematology, leucocyte counts and urinalysis will be taken at the times indicated in the Study Plan ([Table 3](#)).

Blood samples will be analysed at a central laboratory with the exception of leucocyte counts. Due to rapid degradation of neutrophils, leucocyte counts will be performed promptly in local laboratories within 2 hours (maximum 4 hours) of sample collection. Additional leucocyte (including neutrophil) counts will also be analysed at the central laboratory at intervals between receipt of sample and 72 hours after sampling to investigate leucocyte stability.

Urine will be tested locally using dipsticks. In addition, samples will be sent to the central laboratory for urine microscopy and quantitative measurements of total protein, albumin and creatinine if the local dipstick test for protein and/or blood is positive or if the urine sample appears abnormal on macroscopic examination, eg, if it is cloudy.

The central laboratory will provide all the materials required for blood and urine sampling. Instructions for labelling, storage and shipping will be detailed in the laboratory manual.

The laboratory variables to be measured are outlined in [Table 7](#).

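### The fallback reference range in Section 12.2.3 is the local laboratory's, although all blood tests except leucocyte counts are assayed centrally

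*Protocol*

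**What the plan says.** Protocol Section 12.2.3 sets a two-step rule for judging laboratory values. Project ranges come first: "Deviations from extended and standard reference ranges quoted in project reporting ranges, will be explicitly noted on these listings where applicable". The fallback follows: "For parameters where there are no extended or standard reference ranges the reference range from the local laboratory will be used". The same paragraph plans counts of patients outside the reference ranges by time point and treatment group, and separate listings of the out-of-range values.

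Protocol Section 6.4.5 says where each test is run:
- Blood: "Blood samples will be analysed at a central laboratory with the exception of leucocyte counts".
- Leucocytes: "leucocyte counts will be performed promptly in local laboratories within 2 hours (maximum 4 hours) of sample collection".
- Urine dipsticks: "Urine will be tested locally using dipsticks".
- Other urine tests, if the dipstick is positive for protein or blood or the sample looks abnormal: "samples will be sent to the central laboratory for urine microscopy and quantitative measurements of total protein, albumin and creatinine".

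The central laboratory also makes leucocyte counts to study stability. The notes to Table 3 keep these out of the report: "Exploratory leucocyte measurements taken at the central laboratory are for internal modelling use only and will not be reported in the CSR".

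**The concern.** A reference range belongs to a laboratory and its method. Section 12.2.3 falls back on the local laboratory, while Section 6.4.5 gives most of the panel to the central one. A centrally assayed value without a project range would then be called normal or abnormal against limits from a laboratory that never handled the sample.

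Haematology, clinical chemistry and urinalysis are primary outcome variables in Table 1, and Section 12.2.1 plans no hypothesis test. The descriptive counts of patients outside range are therefore part of the primary safety evidence. This is also not a detail left to a later analysis plan: the protocol fixes the rule itself, and a plan that followed it faithfully would carry the mismatch forward.

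**Working it through.** The protocol gives no figure on this point, so there is none to reproduce. The check compares the rule with the place of assay and counts the rows of Table 7.

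**1. Does 'local' mean the analysing laboratory?** The protocol uses local and central as opposed terms in Sections 2.3, 5.4.1, 6.4.5 and 6.7.1.1 and in the notes to Table 3. Table 3 lists safety bloods as haematology without the leucocyte count, plus clinical chemistry. Section 6.4.3 sends repeat liver tests to the central laboratory. No section provides for the central laboratory's range in listings or summaries. The literal reading is the natural one.

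**2. Rows of Table 7 by laboratory that produces the reported result.**

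| Group | Rows | Central | Local |
|---|---|---|---|
| Clinical chemistry | 14 | 14 | 0 |
| Haematology | 4 | 3 (erythrocytes, haemoglobin, platelets) | 1 (leucocytes with differential) |
| Urinalysis | 7 | 4 if triggered (microscopy, albumin, total protein, creatinine) | 3 (dipsticks) |
| Total | 25 | 21 | 4 |

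Blood: 14 + 3 = 17 central rows of 14 + 4 = 18. Urine: 4 central rows of 7. All rows: 17 + 4 = 21 central, 1 + 3 = 4 local.

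**3. Where the rule fits and where it does not.** For the 4 local rows, the fallback names the laboratory that ran the test. For the 21 central rows it does not. The fallback applies only to rows without a project range, and the protocol does not say which those are. The affected number therefore lies between 0 and 17 blood rows and between 0 and 4 urine rows.

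**4. Which outputs depend on the range.** Flags on listings, counts outside range by visit and arm, and the separate out-of-range listings do. Means, medians, SDs and changes from baseline do not. Nor do the stopping limits for neutrophils (below 1.0 x 10^9/L) and leucocytes (below 2.0 x 10^9/L) in Section 5.8, which are fixed numbers.

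**The case against.** The strongest reply is that the fallback may never be used. If every centrally assayed parameter has an extended or standard project range, the sentence affects only the local tests, for which it is right. That stands, and it is why the size is given as a range starting at 0.

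A second reply is that 'local laboratory' is loose wording for whichever laboratory did the work. The consistent contrast between local and central elsewhere in the protocol speaks against this, and the clarification would be needed even so.

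A third reply is that impact is small: no test depends on these displays, and the continuous summaries do not use a range. That also stands.

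Two stronger readings are tempting, and the document supports neither.

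- A reader might infer that, with about 16 sites, one central result could be judged against up to 16 different ranges and distort the arm comparison. The protocol does not say that each site uses a different local laboratory, and it makes no provision for collecting local ranges for centrally assayed analytes. A missing range that has to be queried is at least as likely an outcome.
- A reader might infer a conflict over neutrophils, because Section 5.8 continues blood-count monitoring after withdrawal "until the neutrophil numbers are within the local" laboratory's reference range, while the tables put project ranges first. Section 5.8 uses that range only to say when monitoring after withdrawal ends, and it judges recovery on the repeat sample against the fixed limits above. Section 12.2.3 governs reporting. The two can label a value differently without contradicting each other, and common project ranges for counts made in several local laboratories are a defensible choice.

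**Conclusion.** The mismatch is real and minor. As written, Section 12.2.3 assigns the wrong laboratory's range to any centrally assayed parameter without a project range: 0 to 17 blood rows and 0 to 4 urine rows of Table 7. The exact number cannot be known without the project reporting ranges.

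The conclusion rests on reading 'local' as the protocol uses it elsewhere. Any effect is limited to flags, counts and listings of out-of-range values. The document gives no basis for saying how many patients would be classified differently.

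**What to change.** Replace the fallback sentence in Section 12.2.3 with wording such as:

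*Where a parameter has no extended or standard project range, the reference range of the laboratory that analysed the reported sample will be used: the central laboratory for clinical chemistry, non-leucocyte haematology, urine microscopy and quantitative urine tests; the local laboratory for leucocyte and differential counts and urine dipsticks.*

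The word 'reported' matters because the central laboratory also makes exploratory leucocyte counts that stay out of the study report. No additional neutrophil display is needed.

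The cost is one sentence, plus making sure that the central laboratory's ranges are supplied with its data. If all parameters turn out to have project ranges, nothing is lost. The change should be made before the listings and summaries are produced.
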